### 6.6.1 Treatment of Infusion Reactions

In case of hypersensitivity reactions, the Investigator should institute treatment measures deemed medically appropriate in accordance with current medical practice and treatment guidelines. The following treatment recommendations are based on prior experience with Taxol (containing Cremophor); these and/or other measures deemed medically necessary should be implemented based on the judgment of the Investigator. To reduce the risk of infusion reactions caused by Cremophor, premedication with H1- and H2-blockers (diphenhydramine and ranitidine or equivalents) or dexamethasone (Refer to Section [7.1.2](#) for additional instructions on premedication with steroids) will be given.

Note that the “Grades” listed below do not correspond to NCI CTCAE v5.0 criteria (which are based on response to intervention, and thus are not used here to recommend specific interventions). For the purpose of AE reporting and for determining the need for dose modifications, NCI CTCAE v5.0 grading for allergic reaction should be used.

- Grade 1 allergic reaction/hypersensitivity (e.g., transient flushing, rash, drug fever < 38°C):
  - Supervise at the bedside.
  - Report to Sponsor as an adverse event of special interest (AESI)
- Grade 2 allergic reaction/hypersensitivity (e.g., urticaria, drug fever ≥ 38°C, rash, flushing, dyspnea):
  - Interrupt the infusion and disconnect infusion tubing from patient,
  - Administer IV antihistamines (diphenhydramine 25 to 50 mg), and ranitidine,
  - After recovery from symptoms, resume the infusion at a half of the infusion rate and if no further symptoms appear, complete the administration of the dose. A target infusion time of up to 3 hours may be appropriate in many cases.
  - Report to Sponsor as an AESI
- Grade 3 or 4 allergic reaction/hypersensitivity (e.g., symptomatic bronchospasm requiring parenteral medication(s) with or without urticaria; allergy-related edema/angioedema; anaphylaxis; hypotension):
  - Stop the infusion and disconnect infusion tubing from patient,
  - Administer epinephrine, antihistamines, and nebulized bronchodilators as medically indicated,
  - Consider IV steroids which may prevent recurrent or ongoing reactions,
  - **Report to Sponsor as a serious adverse event (see Section [8.2](#)),**
  - Also report to Sponsor as an AESI

 Taxol (paclitaxel) label: [https://www.accessdata.fda.gov/drugsatfda\\_docs/label/2011/020262s049lbl.pdf](https://www.accessdata.fda.gov/drugsatfda_docs/label/2011/020262s049lbl.pdf)

Other symptoms associated with hypersensitivity reactions include facial flushing, chest pain and tightness, back pain and GI symptoms, leg pain and cough.

A suggested approach for retreatment after a Grade 3 or greater hypersensitivity reaction despite premedication as above is indicated in Section [Error! Reference source not found.](#). Such cases should be discussed between the Sponsor/Medical Monitor and Investigator prior to retreatment.

## 6.6.2 Guidelines for Management of Diarrhea

The following are guidelines for the management of diarrhea and are not meant to replace the clinical judgment of the Investigator / treating physician(s) or an institutional diarrhea management protocol which adheres to most current medical standards.

### 1. Treat with loperamide

Loperamide should be started at the earliest sign of (1) a poorly formed or loose stool, (2) the occurrence of 1 to 2 more bowel movements than usual in 1 day, or (3) an increase in stool volume or liquidity. Loperamide may be taken in the following manners: 4 mg at the first onset of diarrhea, then 2 mg every 2 hours around-the-clock until diarrhea free for at least 12 hours. Patients may take loperamide 4 mg every 4 hours during the night. This dosing regimen is higher than the standard dose of loperamide, but is typical for the treatment of diarrhea caused by anticancer therapy ([Real, 2009](#)). These doses should not be used for more than 48 hours due to the risk of paralytic ileus. Patients should be provided with loperamide at the initial treatment visit so that they have sufficient supply on hand in case antidiarrheal support is required. It is important that loperamide is taken as instructed, as some cases of higher-grade diarrhea have occurred in patients not taking the maximum doses, and these cases have improved after loperamide was taken more frequently. For patients who cannot tolerate loperamide or do not get adequate relief with maximum doses, standard doses of LOMOTIL® (diphenoxylate/atropine) may be added or used instead of loperamide. Additional antidiarrheal measures, such as octreotide, may be used at the discretion of the Investigator or treating physician.

### 2. Interrupt AL101 dosing

For Grade 2 or higher diarrhea that is not controlled (i.e., to Grade 1) with loperamide, dosing of AL101 should be interrupted, as continued dosing is likely to result in increased severity of diarrhea. In addition, evaluation of infectious causes should be considered. Based on the mechanism of action and preliminary clinical experience, full gastrointestinal (GI) tract recovery will likely take longer than the time for diarrhea to resolve. Thus, interruption for 5 days to 7 days beyond the resolution of diarrhea should be considered. Depending on the severity, time to onset, and time to resolution of diarrhea, reduction of AL101 dose and/or frequency, omission of future doses, or dexamethasone co-administration should be considered.

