## **6.6 DOSE MODIFICATION AND TOXICITY MANAGEMENT GUIDELINES**

Dose modification associated with AL101 is described below in [Table 6](#).

The causality assessment system proposed by the World Health Organization Collaborating Centre for International Drug Monitoring, the Uppsala Monitoring Center (WHO-UMC) will be used by the Investigator for assessing drug-related (certain, probable/likely, possible) non-hematological Grade 3 (except isolated Grade 3 electrolyte abnormality that are not associated with clinical signs or symptoms and are reversed with appropriate medical intervention within 48 hours) and hematological Grade 4 toxicities will lead to a 1 dose level reduction for AL101. For easily manageable Grade 1 or 2 toxicity, no dose reductions are required, but careful observation and treatment is required. Dose modification of intolerable Grade 2 toxicity will be evaluated on a case-by-case basis with the Sponsor. Re-escalation of the dose following a dose reduction is allowed only after discussion and approval of the Sponsor's Medical Monitor. Maximum AL101 treatment interruption allowed is 28 days; treatment interruption longer than 28 days will result in discontinuation of patient from the study. Additional treatment guidelines may be implemented by the Investigators, with agreement of the Sponsor/Medical Monitor, as needed to ensure patient safety.

 "The use of the WHO-UMC system for standardized case causality assessment" a communication by WHO-UMC in 2011; [https://www.who-umc.org/media/164200/who-umc-causality-assessment\\_new-logo.pdf](https://www.who-umc.org/media/164200/who-umc-causality-assessment_new-logo.pdf)

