	
improvement within 3 days with maximum doses of loperamide:
 
 
• Patient may be treated with dexamethasone at a dose of 8 mg every 8 hours (Q8h) for up to 5 days. If still no improvement in symptoms, the patient may continue with the dexamethasone or consider switching to budesonide 9 mg once daily (QD). Refer to Section 7.1.2 for additional instructions on premedication with steroids.
 
 
Dose modifications for AL101:
 
Interrupt AL101 until resolution to <math>\leq</math> Grade 1 (refer to Section 7.1.2 for management guidelines for diarrhea and above for management guidelines for diarrhea).
 
Decrease AL101 dose to 2.4 mg QW.
 
If the diarrhea does not resolve to Grade 1 by 14 days, the patient will be discontinued from AL101 (refer to Section 4.5 for early withdrawal of patients from therapy or assessment).
 
If treatment interruption is longer than 28 days, the patient will be discontinued from AL101 (refer to Section 4.5 for early withdrawal of patients from therapy or assessment).
	
improvement within 3 days with maximum doses of loperamide:
 
 
• Patient may be treated with dexamethasone at a dose of 8 mg Q8h for up to 5 days. If still no improvement in symptoms, the patient may continue with the dexamethasone or consider switching to budesonide 9 mg QD. Refer to Section 7.1.2 for additional instructions on premedication with steroids.
 
 
Dose modifications for AL101:
 
Interrupt AL101 until resolution to <math>\leq</math> Grade 1 (refer to Section 7.1.2 and above for management guidelines for diarrhea).
 
Change dose regimen to 6 mg 2 weeks on / 1 week off for first episode
 
Decrease AL101 dose to 4 mg QW for second episode and to 2.4 mg QW for third episode.
 
If the diarrhea does not resolve to Grade 1 by 14 days, the patient will be discontinued from AL101 (refer to Section 4.5 for early withdrawal of patients from therapy or assessment).
 
If treatment interruption is longer than 28 days, the patient will be discontinued from AL101 (refer to Section 4.5 for early withdrawal of patients from therapy or assessment).

Grade 3 diarrhea	Guidelines for the management of diarrhea:	Guidelines for the management of diarrhea:

Confidential

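### For Grade 2 diarrhea that loperamide controls, Table 6 makes an AL101 modification mandatory while Sections 6.6 and 6.6.2 leave it optional, and the protocol does not say which text governs

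*Protocol*

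**What the plan says.** Three places in the protocol bear on a patient whose Grade 2 diarrhea comes down to Grade 1 on loperamide.

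- **Table 6, Grade 2 diarrhea row.** Under a separate sub-heading for AL101 dose modifications, both cohort columns begin "Interrupt AL101 until resolution to" Grade 1 or lower. Cohort 1 then has "Decrease AL101 dose to 2.4 mg QW". Cohort 2 has "Change dose regimen to 6 mg 2 weeks on / 1 week off for first episode", with step-downs to 4 mg and 2.4 mg QW for second and third episodes. None of these lines depends on loperamide having failed.
- **Section 6.6.2, item 2.** "For Grade 2 or higher diarrhea that is not controlled (i.e., to Grade 1) with loperamide, dosing of AL101 should be interrupted". On what follows, it says that "reduction of AL101 dose and/or frequency, omission of future doses, or dexamethasone co-administration should be considered", depending on severity and timing. It also says that "interruption for 5 days to 7 days beyond the resolution of diarrhea should be considered". The opening of 6.6.2 states that its guidelines "are not meant to replace the clinical judgment of the Investigator / treating physician(s) or an institutional diarrhea management protocol".
- **Section 6.6, introductory text.** "For easily manageable Grade 1 or 2 toxicity, no dose reductions are required". Intolerable Grade 2 toxicity is to be settled case by case with the Sponsor. The same section refers to Table 6 for AL101 dose modification and allows re-escalation with the Medical Monitor's approval.

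None of the three places says which prevails if they differ.

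**The concern.** Two sites could each follow the protocol and treat identical patients differently. One, working from Table 6, lowers the dose or thins the schedule after the first Grade 2 episode. The other, working from Sections 6.6 and 6.6.2, sees the event settle on loperamide and leaves the regimen unchanged.

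Diarrhea is not a rare event here. Section 1.3.2 lists it among the adverse events reported by more than 30% of treated patients in the interim data. Section 1.4.1 cites the GI toxicity guidelines as one of the grounds for adding the 6 mg cohort. If those guidelines are read in two ways, dose intensity, later diarrhea rates and possibly response within a cohort reflect the paragraph followed as well as the assigned dose.

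The planned exposure summaries would show this only in part. SAP Section 7.8.1 covers total AL101 received, infusions not given as planned with reasons, and reductions from 6 to 4 mg or 4 to 2.4 mg. It names no summary of the change to 2 weeks on / 1 week off.

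**Working it through.** **Step 1. The texts side by side, for AL101-related Grade 2 diarrhea brought to Grade 1 by loperamide (first episode).**

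| | Table 6 | Section 6.6.2 | Section 6.6 |
|---|---|---|---|
| Interrupt? | Yes, until Grade 1 or lower | Called for when loperamide has not achieved control; no instruction to interrupt otherwise | Not addressed in the general Grade 1 or 2 rule |
| Modify dose or schedule? | Yes, stated without condition | To be considered | No dose reduction required if easily manageable |
| Status | Section 6.6 refers to it for dose modification | Guidelines that yield to clinical judgment or an institutional protocol | General rule |

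**Step 2. Does Table 6 contain a hidden loperamide condition?** The Grade 2 cells do have a clause about earlier measures not having worked, but it introduces the dexamethasone step. It also lists progression to Grade 2 as an alternative trigger, so it would not exempt a controlled Grade 2 event. The AL101 modifications come afterwards under their own sub-heading.

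**Step 3. Where do the texts really differ?** On modification, Table 6 differs from both other texts. On interruption the practical gap is small: dosing is weekly, and an event back at Grade 1 before the next infusion already meets Table 6's condition for resuming.

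**Step 4. Do the cross-references settle it?** For diarrhea management, the Grade 2 cells for both cohorts and the Grade 3 cell for Cohort 2 cite Section 7.1.2, which is premedication with corticosteroids. Only the Grade 3 cell for Cohort 1 cites Section 6.6.2. All four also point to the guidance higher up in the same cell. The references therefore disagree with each other and establish no order of precedence.

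**Step 5. Size per affected patient.** The doses come from Table 6.

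- Cohort 1: 4 mg per week if unchanged, 2.4 mg if Table 6 is followed. 1 − 2.4/4 = 0.40, so 40% lower.
- Cohort 2, first episode: 6 mg per week if unchanged. On 2 weeks on / 1 week off, 6 × 2/3 = 4 mg per week on average. 1 − 4/6 = 0.33, so 33% lower.

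As an illustration, assume 24 weeks of treatment, the change made after dose 4, no missed doses and no re-escalation:

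- Cohort 1: 4 × 4 + 20 × 2.4 = 64 mg, against 24 × 4 = 96 mg (67%).
- Cohort 2: 4 × 6 + 20 × 4 = 104 mg, against 24 × 6 = 144 mg (72%), using the average weekly dose after the change.

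**Step 6. Number of patients.** This would need the Grade 2 diarrhea rate and the share of those events controlled by loperamide. The documents give neither. The figure above 30% is for any grade and regardless of causality, whereas Table 6 covers AL101-related events. No count is derived.

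**The case against.** The best defence is that precedence can be inferred. Section 6.6 refers to Table 6 for dose modification, Section 6.6.2 calls itself guidelines, and the table invites questions to the Medical Monitor. A specific table alongside advisory text is ordinary protocol structure. This has some force against Section 6.6, which is general. It has less against Section 6.6.2, which is just as specific to diarrhea and is cited by one of Table 6's own diarrhea cells. The inference is reasonable, but the protocol never states it.

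Several other objections stand and limit the point:

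- A reader might infer three mutually conflicting rules. The documents do not support that: Sections 6.6 and 6.6.2 are compatible with each other, and each differs from Table 6.
- A reader might infer conflicting restart rules. The hold of 5 to 7 days is discretionary and follows an interruption for uncontrolled diarrhea, so it does not concern the patient considered here.
- For a first episode in Cohort 2, the clash with Section 6.6 is weaker. That section speaks of dose reductions, while Table 6 keeps 6 mg per infusion and changes the schedule. The clash with Section 6.6.2 remains, because that text makes a reduction in frequency, too, a matter for consideration.
- A reader might infer that GI control was the sole basis for the 6 mg cohort. Section 1.4.1 also cites the overall safety profile, liver monitoring, the Phase 1 data and the pharmacodynamic results.

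**Conclusion.** The inconsistency is real and should be corrected. For Grade 2 diarrhea controlled by loperamide, Table 6 makes modification of AL101 mandatory, Section 6.6.2 makes it discretionary, and Section 6.6 requires no dose reduction if the event is easily manageable. No text says which governs.

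The consequence per affected patient is a planned weekly dose 40% lower in Cohort 1 or 33% lower in Cohort 2 under one reading than under the other. This assumes that the alternative reading leaves the regimen unchanged, and it lasts until any re-escalation that the Medical Monitor approves. The number of patients affected is unknown.

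Variation between sites is a foreseeable result of the wording; the documents do not show that it has occurred. Nor do they support a claim that the trial's response results are distorted by a known amount. Each cohort is analysed separately, and total dose received will be summarised. This is a defect of wording, and nothing here judges which dosing rule is right.

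**What to change.** - Reconcile the Grade 2 diarrhea row of Table 6 with Sections 6.6 and 6.6.2, so that all three state the same condition for interruption and the same condition for modification, including whether control by loperamide matters.
- State which text governs if they differ, and how that fits with the latitude that Section 6.6.2 gives to institutional protocols.
- Make the diarrhea-management cross-references the same in all four Grade 2 and 3 dose-modification cells, pointing to whichever text the sponsor designates.

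The choice of rule belongs to the sponsor. The cost is protocol wording only, with no new visits, assessments or data collection.

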### 3. Increase fluid intake and, if applicable, consider stopping antihypertensive therapy and nonsteroidal anti-inflammatory drugs

Hypotension and/or renal insufficiency can occur in the setting of volume depletion from severe diarrhea. At the onset of any diarrhea, patients should be instructed to increase fluid

Confidential

Document State: Effective (Controlled)  
CONFIDENTIAL

Page 63 of 118

intake to help maintain fluid and electrolyte balance during episodes of diarrhea. Parenteral hydration should be started if oral hydration is not sufficient. The investigator should consider interrupting antihypertensive therapy and nonsteroidal anti-inflammatory drugs, if medically appropriate.

#### 4. Treat with dexamethasone

For Grade 2 or higher diarrhea that is not adequately controlled with loperamide and dose interruption, administration of dexamethasone may be considered at the discretion of the treating physician/investigator. In nonclinical models of other GSIs, coadministration of dexamethasone has been shown to decrease the severity of intestinal pathology. (Real, 2009; Wei, 2010). Dexamethasone may be administered per os (PO) or IV, as appropriate. As there is no reported human experience with the use of dexamethasone for this indication, it is not known whether this effect will occur in humans at achievable exposures of dexamethasone. In a small number of cases, administration of dexamethasone 8 mg to 10 mg daily, followed by tapering over several days, may have contributed to the improvement of diarrhea. If, in the judgment of the investigator, it is in the patient's best interest to receive additional treatment with AL101 (for example, the patient has a response to therapy), dexamethasone co-administration with future doses may be used after discussion with the Sponsor/medical monitor. In such cases, dexamethasone 8 mg to 10 mg daily for 2 days to 3 days, beginning on the day of AL101 dosing followed by tapering over several days, may be appropriate.

For diarrhea associated with signs of colitis (e.g., fever, peritoneal signs, or significant GI bleeding), administration of dexamethasone and antibiotics should be considered. Also, inpatient hospitalization, bowel rest, and radiological evaluation may be appropriate if there are signs of possible intestinal perforation.

### 7 STUDY RESTRICTIONS

#### 7.1 PRIOR AND CONCOMITANT THERAPY

##### 7.1.1 Premedication to Prevent Hypersensitivity Reaction

Histamine is a major mediator of anaphylactic/anaphylactoid responses in man, such as those induced by Cremophor EL, an excipient in AL101. The premedication regimen below is based on clinical experience with other compounds containing Cremophor EL.

In order to prevent a hypersensitivity reaction, all patients initiating AL101 treatment will be premedicated approximately 1 hour prior to the infusion of AL101 with the following regimen:

- H1-blocker (for example, diphenhydramine 25 to 50 mg oral or equivalent), and
- H2-blocker (for example, famotidine 20 to 40 mg oral or equivalent).

For patients who remain on study for more than 4 doses of AL101 without any evidence of infusion-related reaction, modification of the premedication regimen may be considered at the discretion of the investigator, with notification of the Sponsor's Medical Monitor. At this time, 1 of the 2 histamine blockers may be discontinued; if there is still no evidence of infusion-related reaction with the next 2 doses of AL101, the other may be discontinued. If under this

Confidential

Document State: Effective (Controlled)  
CONFIDENTIAL

Page 64 of 118

discontinuation plan, the patient has an infusion-related reaction resulting in medical treatment, premedication with H1- and/or H2-blockers (as appropriate) should be resumed for subsequent doses.

If a patient experiences a Grade 3 or 4 infusion-related reaction despite pretreatment with the H1- and H2-blockers then the patient, if re-treated, should also be premedicated with corticosteroids (as described in Section [7.1.2](#)) in addition to the H1- and H2-blockers). In the event that a patient has a repeat Grade 3 or 4 infusion-related reaction despite premedication with H1- and H2-blockers and steroid, the patient must not receive any further treatment with AL101, unless agreed by the Sponsor/Medical Monitor and investigator that it is in the patient's best interest to continue treatment (e.g. patient has had a response to therapy) and appropriate safety measures can be implemented. Such measures may include dose reduction, increased infusion time, initial lower infusion rate with gradual increases, and/or premedication with multiple doses of dexamethasone. These measures have been used to allow re-treatment after infusion reactions with other agents, including IXEMPRA and Taxol ([Peereboom, 1993](#)).

### **7.1.2      Premedication with Corticosteroids**

All patients will receive premedication with corticosteroids as prophylaxis utilizing the approximately following regimen.

- 8 mg dexamethasone Per Os (PO) the night before each infusion
- 8 mg dexamethasone PO or IV within 30 minutes prior to dosing
- 8 mg PO every 8 hours for an additional 4 doses starting about 4 to 8 hours after the infusion is finished
- Repeat for the first 4 doses (first cycle).

If there are no GI toxicities following the first 4 infusions, the number of additional doses following the future infusions can be decreased from 4 to 2 doses of 8 mg PO every 8 hours.

Further tapering should only be considered if, in the opinion of the investigator, steroid side effects are an issue and after discussion with the Sponsor's Medical Monitor.

Other steroids, such as budesonide or prednisone may be used utilizing "prednisone equivalent" conversions.

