Premedication Instructions	As with any medication containing Cremophor, use premedication per the institution guidelines to reduce risk of infusion reactions. For any questions, please contact the Sponsor's Medical Monitor.  Based on prior experience with Taxol (containing Cremophor)  ; these and/or other measures deemed medically necessary should be implemented based on the judgment of the Investigator. To reduce the risk of infusion reactions caused by Cremophor, premedication with H1- and H2-blockers (diphenhydramine and ranitidine or equivalents) or corticosteroids (refer to Section 7.1.2) will be given.
IMP definition	A new drug that is used in a clinical investigation (FDA)
Sourcing	AL101 is manufactured by Bristol-Myers Squibb.  Investigational product will be provided to the site centrally by the Sponsor or designated representative (Fisher Clinical Services, USA).
Packaging and Labeling	AL101 is supplied as a single-use sterile solution 5 mL per vial (1.2 mg/mL; equivalent of 6 mg per vial) for IV administration; The secondary packaging and labeling of investigational product will be performed by Fisher Clinical Services.  All packaging and labeling operations for investigational product will be performed according to Good Manufacturing Practices for Medicinal Products and the relevant regulatory requirements. Label text for the AL101 vial will at a minimum include the protocol number, the contents of the vial, lot number, storage conditions, and Sponsor name and address.
Former Name(s) or Alias(es)]	BMS-906024

For pre-medication instructions, refer to Section **Error! Reference source not found..**

Additional information is provided in the AL101 Study Pharmacy Manual.

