### **7.1.3      Allowed Medications**

All treatments that the Investigator considers necessary for a patient's welfare may be administered at the discretion of the Investigator in keeping with the community standards of medical care. All concomitant medication will be recorded on the eCRF including all prescription, over-the-counter (OTC), herbal supplements, and IV medications and fluids. If changes occur during the study period, documentation of drug dosage, frequency, route, and date may also be included on the eCRF.

All concomitant medications received within 28 days before the first dose of investigational product and 30 days after the last dose of investigational product should be recorded.

Confidential

Document State: Effective (Controlled)  
CONFIDENTIAL

Page 65 of 118

Concomitant medications administered after 30 days after the last dose of investigational product should be recorded for SAEs and AESIs as defined in Section 8.4. In addition, all prior therapies for ACC should be recorded.

Allowed concomitant therapies:

- Glucocorticoids may be administered for treatment of infusion reaction and as premedication to prevent further infusion reaction (maximum daily dose of prednisone or equivalent  $\leq$  10 mg/day).
- In Cohort 2, in case of toxicity (e.g., GI AEs), per discretion of the Investigator and in consultation with the Sponsor's Medical Monitor, dexamethasone (Refer to Section 7.1.2) will be permitted.
- Palliative radiation therapy to a limited field (e.g., painful bone metastasis, painful lumps), *if it is not the sole site of measurable and/or assessable disease*, is allowed any time during study participation with prior approval of the Sponsor's medical monitor.
- Patients with castration resistant prostate cancer who have not undergone surgical orchiectomy can continue on medical therapies (i.e., gonadotropin releasing hormone [GnRH] analogs) to maintain castrate levels of serum testosterone. Concurrent treatment with ketoconazole or anti-androgens is not permitted, and patients who have discontinued these medications must have a washout period of at least 4 weeks or 5 half-lives of the drug (whichever is longer) prior to the first dose of investigational product.

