#### 7.1.4 Prohibited Concomitant Medication

Medications specifically prohibited in the exclusion criteria are not allowed during the ongoing study. If there is a clinical indication for any medication or vaccination specifically prohibited during the study, discontinuation from study therapy or vaccination may be required. The Investigator should discuss any questions regarding this with the Sponsor's Medical Monitor. The final decision on any supportive therapy or vaccination rests with the Investigator and/or the patient's primary care physician. However, the decision to continue the patient on study therapy or vaccination schedule requires the mutual agreement of the Investigator, the Sponsor and the patient.

Patients are prohibited from receiving the following therapies during the Screening and Treatment periods (including retreatment for post-complete response relapse) of this study:

- Prior treatment with gamma secretase inhibitors.
- Note: the following situations are considered 1 line of therapy:
  - *Discontinuation of one drug in a multi-drug regimen and continuation of (an) other drug(s).*
  - *Restarting the same regimen after a drug holiday.*
  - *Switching from IV to oral formulation of the same drug is also considered one regimen.*

Confidential

Document State: Effective (Controlled)  
CONFIDENTIAL

Page 66 of 118

- Exposure to any investigational drug within 4 weeks or 5 half-lives whichever is longer or concurrently with investigational product administration.
- Chronic systemic glucocorticoid use (high dose defined as > 10 mg/day prednisone or equivalent).
- Use of any herbal supplements within 1 week prior to investigational product administration.
- Use of medications causing Torsades de Pointes within 1 week or 5 half-lives (whichever is longer; see [Appendix A](#)).
- Use of strong inhibitors of CYP3A4 within 1 week or 5 half-lives (whichever is longer) or strong inducers of CYP3A4 within 2 weeks or 5 half-lives (whichever is longer; see [Appendix B](#)).
- At least 6 months must have elapsed after prior therapy with any investigational nucleoside analogue.

Patients who, in the assessment by the Investigator, require the use of any of the aforementioned treatments for clinical management should be removed from the study. Patients may receive other medications that the Investigator deems to be medically necessary.

The Exclusion Criteria describes other medications that are prohibited in this study.

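### Protocol 7.1.2 requires dexamethasone premedication at doses above the 10 mg/day prednisone-equivalent cap in 7.1.3, and the text does not reconcile the two

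*Protocol*

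**What the plan says.** **The regimen.** Protocol 7.1.2 opens with "All patients will receive premedication with corticosteroids as prophylaxis utilizing the approximately following regimen" and has no cohort restriction. It lists "8 mg dexamethasone Per Os (PO) the night before each infusion", then "8 mg dexamethasone PO or IV within 30 minutes prior to dosing", then four further 8 mg doses at 8-hour intervals, the first about 4 to 8 hours after the infusion ends. After four infusions without GI toxicity, the four later doses may fall to two. Further tapering is considered only for steroid side effects, after discussion with the medical monitor.

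**The cap.** Protocol 7.1.3 allows glucocorticoids for treating an infusion reaction and "as premedication to prevent further infusion reaction (maximum daily dose of prednisone or equivalent" at most 10 mg/day). A separate item permits dexamethasone in Cohort 2, citing 7.1.2, in case of toxicity, at the investigator's discretion and in consultation with the medical monitor.

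**The prohibition.** Protocol 7.1.4 lists "Chronic systemic glucocorticoid use (high dose defined as > 10 mg/day prednisone or equivalent"). It adds that patients who, in the investigator's assessment, "require the use of any of the aforementioned treatments for clinical management should be removed from the study". *Chronic* is not defined, and no exception for 7.1.2 is written.

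**Other passages on who receives steroid.**
- Table 5 in Protocol 6.1 gives "premedication with H1- and H2-blockers (diphenhydramine and ranitidine or equivalents) or corticosteroids". The synopsis, Table 6 (Grade 2 infusion-related reaction), Protocol 6.6.1 and SAP 6.3.1 use the same *or* structure with dexamethasone.
- Protocol 7.1.1 says that a patient with a Grade 3 or 4 reaction despite H1- and H2-blockers, "if re-treated, should also be premedicated with corticosteroids", as 7.1.2 describes.
- Protocol 6.6.2 makes dexamethasone with later AL101 doses optional, after discussion with the sponsor.

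**The concern.** One section obliges sites to give a steroid regimen. The next limits steroid premedication to a daily amount that the regimen appears to exceed several-fold, and treats dexamethasone in Cohort 2 as something permitted when toxicity occurs. A site that reads 7.1.2 literally and a site that reads 7.1.3 literally would give very different exposure.

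Steroid exposure is not incidental here. Protocol 1.3.2 and 1.4.1 rest the 6 mg cohort partly on rigorous management of GI toxicity. Protocol 6.6.2 describes dexamethasone as possibly contributing to improvement of diarrhea. Safety and tolerability is a secondary objective in Protocol 2. If sites resolve the conflict differently, rates of diarrhea and infusion reaction, and the apparent tolerability of each dose, would partly reflect which passage a site followed.

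**Working it through.** The documents state no daily total or prednisone equivalent for the 7.1.2 regimen, so there is no figure to reproduce. The check has two parts: whether the regimen exceeds the cap, and whether the two govern the same use.

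**Inputs**
- 8 mg per dose: one dose the night before, one before infusion, four afterwards (later reducible to two), from Protocol 7.1.2.
- Weekly infusion over 60 minutes, from Table 5.
- Cap of 10 mg/day prednisone or equivalent, from Protocol 7.1.3. The same threshold defines high dose in 7.1.4.
- Dexamethasone-to-prednisone factor: **not given**. Assumed range 5 to 7.5, with 1 as an extreme lower bound.

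**Dose per infusion**
- Full: (1 + 1 + 4) × 8 = 48 mg dexamethasone.
- Reduced: (1 + 1 + 2) × 8 = 32 mg.

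**Dose on the infusion day**
- Infusion starts between 08:00 and 14:00 were tried, with the first later dose 4 to 8 hours after the end. The calendar day then holds the pre-infusion dose plus one or two later doses: 2 × 8 = 16 mg to 3 × 8 = 24 mg. This holds for both the full and the reduced regimen.
- During 8-hourly dosing, 24 hours contain 3 × 8 = 24 mg.

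**Comparison with 10 mg/day**

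| Factor | Infusion day (16 to 24 mg) | Multiple of cap |
|---|---|---|
| 1 | 16 to 24 mg | 1.6 to 2.4 |
| 5 | 80 to 120 mg | 8 to 12 |
| 7.5 | 120 to 180 mg | 12 to 18 |

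A single 8 mg dose exceeds the cap for any factor above 10/8 = 1.25.

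**Weekly average** (relevant only to the chronic-use threshold)
- Full: 48/7 = 6.9 mg/day dexamethasone, or 34 to 51 mg/day prednisone equivalent at factors 5 to 7.5. It passes 10 mg/day only if the factor exceeds 10/(48/7) = 1.46.
- Reduced: 32/7 = 4.6 mg/day, or 23 to 34 mg/day. The factor must exceed 10/(32/7) = 2.19.

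**Do the regimen and the cap govern the same use?**
- The 7.1.3 cap covers treatment of an infusion reaction and premedication against further ones.
- Table 6 (after a Grade 2 reaction) and Protocol 7.1.1 (after a Grade 3 or 4 reaction) both point to 7.1.2 for the steroid. That is premedication against a further reaction, which is exactly what the cap covers.
- The synopsis, Table 5 and Protocol 6.6.1 also cite 7.1.2 for reducing the risk of Cremophor infusion reactions.
- The Cohort 2 item in 7.1.3 cites 7.1.2 as a permission tied to toxicity, while 7.1.2 already requires that steroid of everyone.

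The scopes overlap, and in the overlap the dose exceeds the cap on infusion days whatever conversion factor of 1 or more is used.

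**The case against.** The best defence is that the two sections serve different purposes. The 7.1.2 step-down depends on GI toxicity, which suggests prophylaxis for the gut, while the 7.1.3 cap concerns *further* infusion reactions. This has some force for a patient who has had no reaction, because it is then unclear whether the cap applies. It does not remove the conflict, because the protocol itself sends sites to 7.1.2 for premedication after a reaction.

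A reader might infer that no site can comply with 6.1, 7.1.1, 7.1.2, 7.1.3 and 7.1.4 together. The documents do not support that. The *or* in Table 5 does not forbid giving both. Protocol 7.1.1 says steroid should be added after a severe reaction, not that it is withheld before one. A site giving H1- and H2-blockers and 7.1.2 steroid to everyone breaches neither. These passages are unclear beside 7.1.2, not incompatible with it.

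A reader might also infer that following 7.1.2 is prohibited and requires removal under 7.1.4. That prohibition concerns chronic use, undefined, and 7.1.2 describes short courses around each infusion. The protocol directs high-dose steroid elsewhere: dexamethasone 8 mg every 8 hours for up to 5 days in Table 6, and prednisone 1 to 2 mg/kg/day in Table 10. Reading 7.1.4 as barring protocol-directed steroid would bar those too. What stands is that 7.1.2 recurs with every infusion and no exception is written, so the relation between the sections is left to interpretation.

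**Conclusion.** The point holds as an internal contradiction between current passages. The premedication required by 7.1.2 carries 16 to 24 mg dexamethasone on a daytime infusion day. Where it is used against further infusion reactions, it exceeds the 10 mg/day cap in 7.1.3 by a factor of 8 to 18 under the assumed conversion of 5 to 7.5, and still exceeds it at 1:1. The Cohort 2 permission in 7.1.3 also does not fit a regimen required for all patients. The remaining passages are ambiguous and need aligning, but can be followed together.

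Three limits apply:
- It is not shown that every treated patient is affected. The safety set already held 29 patients by October 2019. The amendment of 27 August 2020 reorganized and added premedication sections, and the documents do not say which text governed earlier dosing.
- A reader might infer that the Per-Protocol set will change. Nothing says that giving or omitting 7.1.2 steroid would be coded as a major deviation. Those are for the sponsor to define before database lock (SAP 7.2 and 7.3.2), so this is an open question and not a demonstrated effect.
- The primary ORR analysis uses the Efficacy Evaluable set (SAP 7.5.2). That analysis, the power and the type I error are untouched.

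What is at stake is site-level clarity on a safety measure, and interpretation of GI toxicity, infusion reactions and tolerability.

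**What to change.** The sponsor must reconcile the synopsis (Investigational Product Route and Dosage Form), Table 5, Table 6, Protocol 6.6.1, 6.6.2, 7.1.1, 7.1.2, 7.1.3 and 7.1.4, and SAP 6.3.1. Together they should state one consistent premedication rule, its relation to the 7.1.3 cap and the Cohort 2 item, and its relation to the 7.1.4 prohibition, including what counts as chronic use. Which rule or dose should prevail is a clinical decision for the sponsor, and none is proposed here.

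Deviation coding for steroid premedication should then be defined consistently with the reconciled text before database lock. If dosing is already complete, that coding rule and a description in the study report of the steroid actually given are what remain useful.

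The cost is small: a protocol clarification or letter to sites, a matching line in the SAP, and one deviation-coding rule. No change to sample size or to the primary analysis is needed.
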